### 5.2. Analyses methods

The main analyses for primary and secondary outcomes will follow the intention-to-treat approach. For the primary outcome, given the commonly observed non-normality distribution of the data in this fields, a Mann-Whitney U test will be used to compare the median CCI between the intervention and control groups. For secondary outcomes with a single time-point (e.g., hospital lenght of stay), comparisons between groups will also be conducted using Mann-Whitney U test. To assess whether the group allocation (intervention/control) influences the risk of postoperative complications (yes/no), a binary logistic regression model will be conducted. Regarding secondary outcomes at multiple time points, a linear mixed-effects models with individual measures of growth being modelled as the function of randomly assigned group, assessment time, and the interaction between group and time. Estimations will be performed using the restricted maximum-likelihood method, including an unstructured covariance matrix to adjust for within-participant clustering resulting from the repeated-measures design. This model will assume that missing values are missing-at-random.

Secondary analyses will be performed using the per-protocol approach, defined as attending >80% of the sessions offered to the intervention group.

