## 2.2. Randomization

After concluding baseline assessments, eligible participants will be randomly assigned (1:1 allocation) to either the control or intervention group by means of computer generated simple, unrestricted randomization.

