#### 4.5. Baseline patients' characteristics

A baseline table will be created to describe the characteristics of the study population. The characteristics include general characteristics (e.g., age or sex), anthropometry and body composition (e.g., body weight, height, body mass index or waist circumference), cardiometabolic health (e.g., glycaemic or lipid profile), physical fitness (e.g., cardiorespiratory fitness or muscular strength), tumour stage and surgery characteristics (e.g., type of surgery or duration of surgery). The characteristics of the total study population and each study arm will be summarized using mean (SD) or median (interquartile range) for normally and not normally distributed continuous variables, respectively, and as number (percentage) for categorical variables.

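### The CCI and complication comparisons name no baseline covariates in a simply randomised trial of 90 patients: valid tests, but an avoidable loss of precision

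*SAP*

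**What the plan says.** - **Allocation (SAP 2.2).** After the baseline assessments, "eligible participants will be randomly assigned (1:1 allocation) to either the control or intervention group". The method is "computer generated simple, unrestricted randomization", so there are no blocks and no strata.
- **Primary analysis (SAP 5.2).** For CCI, "a Mann-Whitney U test will be used to compare the median CCI between the intervention and control groups".
- **Complications (SAP 5.2).** To assess whether group allocation "influences the risk of postoperative complications (yes/no), a binary logistic regression model will be conducted". Group is the only predictor named. The text neither lists covariates nor rules them out.
- **Baseline data (SAP 4.5).** "The characteristics include general characteristics (e.g., age or sex), anthropometry and body composition"; the list goes on to "physical fitness (e.g., cardiorespiratory fitness or muscular strength), tumour stage and surgery characteristics". Their only stated use is a descriptive table.
- **Elsewhere.** The regressions and partial correlations in section 5.4 are introduced as cross-sectional analyses of baseline data, not as treatment comparisons. The mixed models for repeated secondary outcomes do use the baseline measurement, as one of the time points. CCI and complications have no such link to baseline.

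**The concern.** Neither the design nor the analysis of the primary outcome uses prognostic information. Balance on age, sex and fitness is left to chance, and the CCI test cannot take account of whatever imbalance results. The repeated secondary outcomes therefore draw more on the baseline data than the primary outcome does.

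Two things are at stake. The first is precision: in a small trial, variation in CCI that baseline values could explain stays in the error term. The second is credibility. If a visible imbalance appears in the baseline table, the SAP has no pre-specified adjusted result to set beside the unadjusted one, and any adjustment would then be chosen after seeing the data.

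**Working it through.** **Inputs from the SAP.** Difference 17.3 CCI points, SD 25.2, α 0.05, 90% power, 36 per group before and 45 per group after a 20% drop-out allowance (section 2.3). Two-tailed tests (3.1). All randomised participants analysed (3.3). No missing data expected for the prognostic variables taken from medical records (5.3).

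**Assumption not in the SAP.** R², the share of CCI variation explained by the covariates. No document figure links age, sex or walk distance to CCI, so a range is shown.

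**1. The plan's own figure.** n per group = 2 × [25.2 × (1.960 + 1.282) / 17.3]² = 44.6, so 45. The stated 36 does not reproduce for a two-sided test at 90% power. That is a separate matter and is not counted here. The drop-out step does reproduce: 36 / 0.8 = 45.

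**2. Sample size for CCI.** Sections 3.3 and 5.3 together put the CCI analysis near 45 per arm, so 45 is used below.

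**3. Power with adjustment.** The residual SD becomes 25.2 × √(1 − R²), and power = Φ(17.3 / [25.2 × √(1 − R²) × √(2/45)] − 1.960). With R² = 0 the standard error is 25.2 × 0.2108 = 5.31 points and the ratio is 3.256.

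| Assumed R² | Ratio | Power |
|---|---|---|
| 0 | 3.256 | 90.3% |
| 0.02 | 3.289 | 90.8% |
| 0.05 | 3.341 | 91.6% |
| 0.10 | 3.433 | 93.0% |
| 0.20 | 3.641 | 95.4% |

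Over R² 0.05-0.20 the gain is 1.3 to 5.1 points. At R² 0.02 it is about half a point.

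**4. Chance imbalance.** The standardised difference of a continuous covariate has standard error √(2/45) = 0.211. The probability of a difference of at least 0.3 SD in either direction is 2 × [1 − Φ(0.3/0.211)] = 15.5%. For a binary factor with 30% prevalence, the exact binomial probability of a difference of 15 percentage points or more is 13.4%.

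**5. What such an imbalance does.** The shift in the CCI difference is 0.3 × √R² × 25.2.
- R² 0.10: 0.3 × 0.316 × 25.2 = 2.4 points, 14% of 17.3.
- R² 0.30: 0.3 × 0.548 × 25.2 = 4.1 points, 24% of 17.3.

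**6. Check on a CCI-like scale.** A bounded score with 45% zeros in the control arm, control SD about 24, a mean difference of about 12 points and 90 simply randomised patients was simulated, with 2,000 runs per setting.

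| Observed rank R² | Mann-Whitney | Rank ANCOVA | Logistic, group only | Logistic, adjusted |
|---|---|---|---|---|
| 0.08 | 84% | 87% | 79% | 82% |
| 0.16 | 84% | 90% | 79% | 85% |
| 0.23 | 85% | 94% | 80% | 89% |

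With no treatment effect, rejection rates were 4.6% to 5.1% for all four tests. The gains exceed those in step 3 partly because unadjusted power starts lower and R² reaches further. They confirm the direction and the error control, not the size to expect in this trial.

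**The case against.** The strongest reply is that nothing here is wrong. A pre-specified unadjusted Mann-Whitney test under simple randomisation holds its type I error and is unbiased over randomisations. Its p-value already allows for chance imbalance, which is part of the sampling variation being measured. The probabilities in steps 4 and 5 are therefore not probabilities of a false conclusion. This stands, and it makes the point one of efficiency and robustness.

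The gain also rests on an assumed R². The SAP's only CCI contrast is between inactive and active patients, yet only inactive patients are eligible. The other eligibility limits may narrow the prognostic spread further. This stands as well: the gain could be negligible.

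Adjustment has costs. Proportional odds adds an assumption and gives a conditional odds ratio. With few events the logistic model can be overloaded: in a simulation with an assumed 20% control risk and about 13 events, three covariates made the log odds ratio overshoot by about 12%, against about 3% unadjusted. This stands and limits the fix.

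Three stronger readings may tempt a reader.
- **A larger gain, taken from 36 per arm.** Section 2.3 calls 36 sufficient after drop-out, but sections 3.3 and 5.3 keep essentially all randomised patients in the CCI analysis.
- **Unequal arm sizes as part of the harm.** Simple randomisation can produce them, but adjustment does not repair them, and a 40/50 split costs almost nothing (power 89.9% against 90.3%).
- **A logistic model restricted to group alone.** The text says only that "a binary logistic regression model will be conducted" and is silent on covariates.

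**Conclusion.** The point holds as an avoidable loss of precision, not as an error. The primary CCI test cannot use the baseline data, the complication model names no covariates, and simple randomisation does nothing to balance prognosis. At 45 per arm, adjustment is worth about 1 to 5 points of power if covariates explain 5-20% of CCI variation, and less if they explain little. A 0.3 SD imbalance in one covariate has a probability of about 15% and would move the estimated difference by about 2.4-4.1 points at R² 0.10-0.30. These figures rest on the SAP's difference and SD, a normal approximation, near-complete CCI data and the assumed R². A reader might infer that the planned result would be biased or its p-value unreliable. The documents do not support that.

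**What to change.** Before unblinding, amend SAP section 5.2 as follows.

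1. Pre-specify a covariate-adjusted analysis of CCI, either rank ANCOVA or proportional-odds regression, with group and a few fixed pre-randomisation covariates such as age, sex and baseline 6-minute walk distance. Add a simple rule for missing baseline values.
2. Report it alongside the unadjusted Mann-Whitney test and state in advance which of the two is primary.
3. List the same covariates for the complication logistic model, and fix in advance the event count below which fewer covariates or a penalised (Firth) fit will be used.
4. Exclude variables that arise after randomisation. Duration of surgery is one, although section 4.5 lists it among the baseline characteristics.

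The cost is SAP wording and one further model, with no extra patients or measurements. The downside is an added modelling assumption and, under proportional odds or logistic regression, an odds ratio conditional on the covariates. Keeping the Mann-Whitney result in the report limits both.

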### 2.3. Sample size

In a previous study, a 17.3-point mean difference was detected in CCI between a group of patients who were physically inactive and a group who were regularly active, both undergoing colorectal cancer surgery (2). Therefore, this study sample size was estimated for an  $\alpha$  level of 0.05 and 90% power to detect a 17.3-point difference in CCI (primary outcome) between usual care and PPP groups, considering an  $\sigma$  of 25.2 (the CCI standard deviation of the group of participants who were physically inactive). Based on this data, a sample of 36 participants per group was considered sufficient for our analysis. However, assuming a 20% drop-out rate, we decided to recruit a total sample size of 45 participants for each study group. Thus, a total of 90 participants ( $n \approx 45$  women) will be enrolled in the ONCOFIT study.

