### 2.7. Timing of outcome assessment

Primary outcome (CCI) and other clinical prognosis outcomes will be assessed 30 days postoperatively, 3 months after the surgery and 1 year after the surgical procedure. All other secondary outcomes will be measured at baseline, preoperatively (i.e., 1 day before surgery), 3 months after surgery, and 1 year after surgery.

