## 3. Statistical principles

### 3.1. Confidence and P values

All statistical tests will be two-tailed, with a significance level set at  $\alpha = 0.05$ . Corresponding 95% confidence intervals will be reported. No adjustments for multiplicity will be applied, as only one primary outcome has been pre-specified and all secondary and exploratory analyses are considered hypothesis-generating.

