procedures outlined by the International Society for the Advancement of Kinanthropometry.

17. **Change in systolic blood pressure** (Baseline, preoperatively, 3 months after surgery and 1 year after surgery). Systolic blood pressure will be assessed by blood pressure monitor.
18. **Change in diastolic blood pressure** (Baseline, preoperatively, 3 months after surgery and 1 year after surgery). Diastolic blood pressure will be assessed by blood pressure monitor.
19. **Change in cardiorespiratory fitness** (Baseline, preoperatively, 3 months after surgery and 1 year after surgery). Cardiorespiratory fitness will be measured by the distance done in 6 minute walking test.
20. **Change in upper limb muscular strength** (Baseline, preoperatively, 3 months after surgery and 1 year after surgery). Upper limb muscular strength will be measured using a digital hand dynamometer.
21. **Change in lower limb muscular strength** (Baseline, preoperatively, 3 months after surgery and 1 year after surgery). Lower limb muscular strength will be assessed by the 30 seconds sit-to-stand test.
22. **Change in lower limb muscular strength** (Baseline, preoperatively, 3 months after surgery and 1 year after surgery). Lower limb muscular strength will be assessed by the 5 times sit-to-stand test.
23. **Change in gait speed** (Baseline, preoperatively, 3 months after surgery and 1 year after surgery). Gait speed will be determined by the 4-meter usual gait speed test.
24. **Change in Health-related quality of life** (Baseline, preoperatively, 3 months after surgery and 1 year after surgery). Health-related quality of life will be assessed through The European Organisation for Research and Treatment of Cancer quality of life questionnaire for patients with colorectal cancer (EORT-QLQ-CR29).
25. **Change in self-reported depression levels** (Baseline, preoperatively, 3 months after surgery and 1 year after surgery). Self-reported depression levels will be measured by Back Depression Inventory-II questionnaire and Hospital Anxiety and Depression Scale.
26. **Change in self-reported anxiety levels** (Baseline, preoperatively, 3 months after surgery and 1 year after surgery). Self-reported anxiety levels will be measured by State-Trait Anxiety Inventory and Hospital Anxiety and Depression Scale.

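### The mixed model for repeated secondary outcomes lets the arms differ at baseline and does not adjust for baseline, so it gives only change-score precision

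*SAP*

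**What the plan says.** Section 5.2 of the SAP says that secondary outcomes at multiple time points are "modelled as the function of randomly assigned group, assessment time, and the interaction between group and time". Estimation is by REML, "including an unstructured covariance matrix to adjust for within-participant clustering resulting from the repeated-measures design". No baseline covariate and no common baseline mean is mentioned there or elsewhere, and the contrast to be reported is not named.

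Section 2.7 makes baseline one of the visits: "All other secondary outcomes will be measured at baseline, preoperatively (i.e., 1 day before surgery), 3 months after surgery, and 1 year after surgery". In section 5.1, secondary outcomes 9 to 44 are worded as changes over these four visits, for example "Change in cardiorespiratory fitness". Section 5.4 carries a similar approach over to other outcomes.

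Section 2.2 sets the order of events: "After concluding baseline assessments, eligible participants will be randomly assigned (1:1 allocation". The method is "computer generated simple, unrestricted randomization", so nothing in the allocation limits chance imbalance.

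**The concern.** Because allocation follows the baseline visit, the two arms have the same true baseline mean on every outcome, and any observed difference is chance. A model with a group effect at all four visits, baseline included, does not use this. It fits a free baseline mean in each arm and subtracts the observed baseline difference in full. Regression to the mean implies that only a fraction ρ of that difference should be subtracted. An unstructured covariance does not repair this, because the fault lies in the mean model.

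Most of the secondary aims (functional capacity, body composition, patient-reported outcomes, blood markers, lifestyle, sleep) rest on these models. In a trial of 90 patients their intervals would be wider than they need to be, and each estimate would carry part of whatever baseline imbalance happened to occur.

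**Working it through.** **Inputs from the SAP.** Four visits including baseline (2.7). 45 recruited per arm, or 36 evaluable after 20% dropout (2.3). Two-sided α = 0.05 (3.1). The SAP gives no precision, correlation or power figure for the repeated outcomes. Its sample size concerns the CCI alone: 36/(1 − 0.20) = 45 reproduces the recruitment figure. The 36 itself comes back (36.3 before rounding) only with a one-sided 5% test. That is a separate matter, and nothing below depends on it.

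**Assumptions.** ρ between 0.3 and 0.9; SD = 1 at every visit.

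**Formulas**, for the arm contrast at one follow-up visit with n per arm:
- As written (group-by-time contrast, free baseline means): variance = 2(1 − ρ) × 2/n.
- Common baseline mean, or baseline as covariate: variance = (1 − ρ²) × 2/n.
- Ratio, adjusted to written: (1 − ρ²)/[2(1 − ρ)] = (1 + ρ)/2.

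With n = 45 and ρ = 0.5: 2 × 0.5 × 2/45 = 0.0444 as written, against 0.75 × 2/45 = 0.0333. With ρ = 0.7: 0.0267 against 0.0227.

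| ρ (assumed) | SE as written | SE, common baseline | Variance ratio | Total the written model would need to match 90 |
|---|---|---|---|---|
| 0.3 | 0.249 | 0.201 | 0.65 | about 138 |
| 0.5 | 0.211 | 0.183 | 0.75 | 120 |
| 0.7 | 0.163 | 0.151 | 0.85 | about 106 |
| 0.9 | 0.094 | 0.092 | 0.95 | about 95 |

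The last column is 90 divided by the variance ratio.

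**Check on the full model.** Exact generalised-least-squares information matrices for the four-visit model, with equal correlation between visits, give these same standard errors at every ρ in the table. With 20% monotone dropout, the variance as written is still 1.44–1.51 times the constrained one at ρ = 0.3, 1.27–1.31 at 0.5, 1.15–1.17 at 0.7 and 1.04–1.05 at 0.9. A simulation of 20,000 trials, comparing change scores with covariance adjustment in which the slope is estimated, gave ratios of 1.30 (ρ = 0.5) and 1.16 (ρ = 0.7). Theory gives 1.33 and 1.18.

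**Power for a 0.5-SD effect (assumed), Φ(0.5/SE − 1.96).**
- 45 per arm, ρ = 0.5: 0.5/0.2108 − 1.96 = 0.41, so 66%; 0.5/0.1826 − 1.96 = 0.78, so 78%.
- 45 per arm, ρ = 0.7: 86% and 91%.
- 36 per arm, ρ = 0.5: SEs 0.2357 and 0.2041, so 56% and 69%.

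**Chance imbalance.** The baseline difference has SD √(4/90) = 0.21. Given an observed difference D, the written contrast is shifted by −(1 − ρ)D. A one-SD imbalance at ρ = 0.5 moves it by 0.5 × 0.21, about 0.1 SD. This accounts for all of the lost precision: 2(1 − ρ) = (1 − ρ²) + (1 − ρ)², which at ρ = 0.5 is 0.0444 = 0.0333 + 0.25 × 0.0444.

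**If another contrast is meant.** If the between-arm difference at a visit is reported from the same model, its SE with complete data is that of follow-up values alone, 0.211 at n = 45. Its variance is 1.33 times the adjusted one at ρ = 0.5 and 1.96 times at ρ = 0.7. On no reading of section 5.2 is baseline adjusted for.

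**The case against.** The strongest reply is that nothing here is invalid. Group, time and their interaction with an unstructured covariance is a standard model, its contrast is unbiased under randomisation, and it fits outcomes defined as changes. Section 3.1 treats all secondary analyses as hypothesis-generating. The only power claim, "90% power to detect a 17.3-point difference in CCI (primary outcome) between usual care and PPP groups", concerns an outcome with no baseline value that is analysed by Mann-Whitney. All of this is correct and limits the severity, but it does not justify giving up precision that the collected data already provide.

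Several narrower points also stand:
- Baseline is in the response, so it is used inefficiently rather than left out altogether.
- Wider intervals and sensitivity to imbalance are one loss seen from two sides, as the decomposition shows.
- The gain is small for highly stable measures; body height, body weight and bone mineral density are plausible examples.
- The 66% and 78% assume 45 complete patients per arm. With the 36 that section 2.3 allows for, both figures are lower, though the gap is about the same.
- The covariate form is not strictly equivalent to the constrained form when baseline values are missing.
- Section 2.5 reports that descriptive results on some secondary outcomes have already been presented, so a change of model should be dated and explained.

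**Conclusion.** The concern holds. As written, the model gives change-score precision for the group-by-time contrast, exactly so with complete data and approximately with dropout. Constraining or adjusting for baseline would cut the variance by 25% at ρ = 0.5, 15% at 0.7 and 5% at 0.9. These values of ρ are assumptions, since the SAP gives none, and the percentages assume equal SDs at baseline and follow-up. With unequal SDs the written variance exceeds the adjusted one by (σ₀ − ρσ₁)² × 2/n, where σ₀ and σ₁ are the baseline and follow-up SDs. This is never negative, so the direction does not depend on that assumption.

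This is a loss of efficiency, not a bias. It affects nearly all of secondary outcomes 9 to 44. It does not affect the CCI, the QOR-15 or other outcomes without a baseline value. The change should be made, but the primary conclusion does not depend on it.

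**What to change.** In section 5.2, constrain the arms to a common baseline mean: fixed effects for time and for group at each post-baseline visit, no group effect at baseline, with REML and the unstructured covariance kept. The preoperative visit comes after randomisation and so keeps its group term. State that the reported result is the group difference at each post-baseline visit with its 95% interval.

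An acceptable alternative is to model post-baseline visits only, with baseline value and its interaction with time as covariates. The constrained form is preferable because it keeps every patient with any measurement, in line with the missing-at-random assumption in sections 5.2 and 5.3.

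The cost is one sentence in the SAP and one changed formula in the R code. No new data are needed. Date the change, give the reason, and make it before any between-arm results on these outcomes are examined.

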### 5.3. Missing data

The number of missing data will be reported, and patterns of missing data will be explored. Based on previous experience, no missing data are expected for prognostic variables, as these will be extracted from medical records and used unless the patient explicitly revokes consent. For other outcomes, we expect that missing data will be assumed as missing at random. Therefore, the linear mixed model analyses will appropriately account for missing data. Nonetheless, once data processing has been completed, we will formally re-evaluate this assumption.

#### 5.4. Additional analyses

Changes in other outcomes will be analyzed using a similar protocol as described by '5.2 Analysis methods' unless others would be more appropriate depending on the outcome. Moreover, cross-sectional analyses will be performed using the baseline data of the RCT. For example, cross-sectional associations will be explored by bivariate and partial correlations. Then, further analyses will be performed using linear and logistic regression depending on the nature of the study variables and research questions. ANOVAs will also be used to test differences in outcomes among groups.

